#### **7.4.3.6. Regulatory Reporting Requirements for SAEs**

Prompt notification by the investigator to GSK of SAEs related to study treatment (even for non- interventional post-marketing studies) is essential so that legal obligations and ethical responsibilities towards the safety of participants and the safety of a product under clinical investigation are met.

The Sponsor has a legal responsibility to notify both the local regulatory authority and other regulatory agencies about the safety of a product under clinical investigation. GSK will comply with country specific regulatory requirements relating to safety reporting to the regulatory authority, Institutional Review Board (IRB)/Independent Ethics Committee (IEC) and investigators.

Investigator safety reports are prepared for suspected unexpected serious adverse reactions according to local regulatory requirements and GSK policy and are forwarded to investigators as necessary.

An investigator who receives an investigator safety report describing a SAE(s) or other specific safety information (e.g., summary or listing of SAEs) from GSK will file it with the IB and will notify the IRB/IEC, if appropriate according to local requirements.

#### **7.4.3.7. Cardiovascular and Death Events**

Investigators will be required to fill out the specific CV event page of the eCRF for the following AEs and SAEs:

- Myocardial infarction/unstable angina
- Congestive heart failure
- Arrhythmias
- Valvulopathy
- Pulmonary hypertension
- Cerebrovascular events/stroke and transient ischemic attack
- Peripheral arterial thromboembolism
- Deep venous thrombosis/pulmonary embolism
- Revascularisation

This information should be recorded in the specific cardiovascular eCRF within one week of when the AE/SAE(s) are first reported. The CV CRFs are presented as queries in response to reporting of certain CV MedDRA terms.

For any cardiovascular events detailed above, whether or not they are considered SAEs, and all deaths, specific Cardiovascular (CV) and Death sections of the eCRF will be required to be completed. These sections include questions regarding cardiovascular (including sudden cardiac death) and non-cardiovascular death.

The CV CRFs are presented as queries in response to reporting of certain CV MedDRA terms. The CV information should be recorded in the specific cardiovascular section of the eCRF within one week of receipt of a CV Event data query prompting its completion.

#### **7.4.3.8. Death Events**

The Death CRF is provided immediately after the occurrence or outcome of death is reported. Initial and follow-up reports regarding death must be completed within one week of when the death is reported.

In addition, all deaths will require a specific death data collection tool to be completed. The death data collection tool includes questions regarding cardiovascular (including sudden cardiac death) and noncardiovascular death.

### **7.4.3.9. Medical Device Deficiencies**

Medical devices (vial adaptor -where applicable-, syringe, and needles) are used in this study as the study intervention.. To fulfill regulatory reporting obligations worldwide, the investigator is responsible for the detecting and documentation of events meeting the definitions of device deficiency that occur during the study with such devices.

The definition of a medical device deficiency can be found in Section [11.2](#)

NOTE: Medical device deficiencies associated with an SAE will be reported together with an SAE form. AEs associated with a medical device deficiency must be documented in the eCRF.

#### **7.4.3.9.1. Time period for Detecting Medical Device Deficiencies**

Medical device deficiencies that result in an incident will be detected, documented, and reported during all periods of the study in which the medical device is used.

If the investigator learns of any device deficiency at any time after a participant has been discharged from the study, and such a device deficiency is considered reasonably related to a medical device provided for the study, the investigator will notify the sponsor within 24 hours.

Medical device deficiencies and any associated AE/SAEs for associated persons (i.e, spouse, caregiver, site staff) will be collected. The associated person will be provided with safety reporting information and an authorization letter.

The method of documenting Medical Device Incidents is provided in Section [11.2](#)

#### **7.4.3.9.2. Follow-up of Medical Device Deficiencies**

Follow-up applies to all participants and associated persons, including those participants who discontinue study treatment or the study

The investigator is responsible for ensuring that follow-up includes any supplemental investigations as indicated to elucidate the nature and/or causality of the deficiency.

New or updated information will be recorded on the original completed form with all changes signed and dated by the investigator.

#### **7.4.3.9.3. Prompt Reporting of Medical Device Deficiencies to the Sponsor**

Device deficiencies will be reported to the sponsor within 24 hours after the investigator determines that the event meets the protocol definition of a device deficiency.

The medical device deficiency report form will be sent to the sponsor by email.

The sponsor will be the contact for the receipt of device deficiency reports.

#### 7.4.3.9.4. Regulatory Reporting Requirements for Device Deficiencies

The investigator will promptly report all device deficiencies occurring with any medical device used for CAB+RPV in the study, as described in Section 11.2 in order for the sponsor to fulfil the legal responsibility to notify appropriate regulatory authorities and other entities about certain safety information relating to medical devices being used in clinical studies.

The investigator, or responsible person according to local requirements (e.g., the head of the medical institution), will comply with the applicable local regulatory requirements relating to the reporting of device deficiencies to the IRB/IEC.

#### 7.4.4. Toxicity Management

Adverse events that occur during the trial should be evaluated by the Investigator and graded according to the Division of AIDS (DAIDS) toxicity scales (See Section 11.2. “Division of AIDS Table for Grading the Severity of Adult and Pediatric Adverse Events”). Additional information regarding detecting, documenting and reporting AEs and SAEs are available in Section 7.4.3 and Section 11.6.

##### 7.4.4.1. Treatment Interruption Due to an Adverse Event

IP may be interrupted at the discretion of the investigator and according to the severity of the AE. If one or more ART medication is held due to toxicity or AEs, all ART medications should be held to reduce the risk of development of resistance taking into account the length of the planned interruptions and the PK half-life of each ART of the regimen, in order to minimize the risk of development of resistance.

No toxicity-related dose reductions of IP will be allowed. IP should be restarted as soon as medically appropriate; in general, for oral dosing, this should be no longer than 14 days after discontinuation (unless Grade 3 or 4 toxicities persist). Any interruption in therapy during the Maintenance Phase, oral dosing, of greater than 7 consecutive days must be discussed with and agreed by the Medical Monitor prior to resumption of therapy. The Medical Monitor must be contacted upon becoming aware of resumption in therapy, if therapy was resumed without prior approval (Section 6.9). **IM dosing is expected to occur during the week in which the participant’s projected visit falls (as according to the first injection visit). An additional (+ or -) 7 day window, from the projected visit date, is allowable for IM dosing but not preferred.** Any interruption outside of this guidance MUST be discussed with the Medical Monitor prior to reinitiating IM IP (see Section 6.9.1).

Guidance is provided below on general participant management and IP interruptions based on the severity of the AE. Information regarding permitted substitutions \ is provided in Section 6.8. All changes in the IP regimen must be accurately recorded in the participant’s eCRF.

**Note:** For participants receiving an ABC-containing product as part of the background regimen during the Long-Term Follow-Up (LTFU) Phase, in the event of a discontinuation of ABC for any reason, re-initiation of this drug should be undertaken with caution. The investigator should obtain a complete history of the events surrounding the discontinuation of the ABC-containing product, evaluate for the possibility of a clinically suspected HSR, and initiate participant management as outlined in the Local Country Prescribing Information, regardless of a participant's *HLA-B\*5701* status. Screening for the presence of *HLA-B\*5701* is recommended prior to reinitiating treatment with ABC-containing products in participants of unknown *HLA-B\*5701* status who have previously tolerated ABC but is not required to confirm study eligibility.

#### **7.4.4.2. Grade 1 or Grade 2 Toxicity/Adverse Event**

Participants who develop a Grade 1 or Grade 2 AE or toxicity may continue study drug at the discretion of the investigator. Participants who choose to withdraw from the study due to a Grade 1 or 2 AE should have study withdrawal and follow-up evaluations completed.

**Participants who develop ALT  $\geq$ 3 times ULN while on study must consult with Medical Monitor prior to initiation or continuation of CAB LA + RPV LA**

#### **7.4.4.3. Grade 3 Toxicity/Adverse Event**

Participants who develop a Grade 3 AE or toxicity should be managed as follows:

- If the Investigator has compelling evidence that the Grade 3 AE or toxicity has not been caused by IP, dosing may continue after discussion with the Medical Monitor.
- Participants who develop a Grade 3 AE or toxicity, which the Investigator considers related or possibly related to the IP, should have the IP withheld and be rechecked each week until the AE returns to Grade 2. Once the AE is Grade  $\leq$ 2, IP may be re-started.
- Should the same Grade 3 AE recur within 28 days in the same participant, the IP should be permanently discontinued and the participant withdrawn from study.
- Participants experiencing Grade 3 AEs requiring permanent discontinuation of IP should be followed weekly until resolution of the AE and to have withdrawal study evaluations completed. A follow-up visit should be performed 2-4 weeks after the last dose of IP. Any participant receiving at least one dose of CAB LA and /or RPV LA who discontinue IP / Withdraw will initiate treatment with HAART and enter the LTFU Phase for 52 weeks of follow up.
- Participants with Grade 3 asymptomatic laboratory abnormalities should be investigated for all potential non-drug related causes, and, following discussion with the Medical Monitor, may continue IP if the Investigator has compelling evidence that the toxicity is not related to IP, with the exception of liver chemistry stopping criteria (See Section 7.4.5.1). Isolated Grade 3 lipid abnormalities do not require withdrawal of IP.

#### 7.4.4.4. Grade 4 Toxicity/Adverse Event

- Participants who develop a Grade 4 AE or toxicity must have IP permanently discontinued. However, if the Investigator has compelling evidence that the AE is not causally related to the IP, dosing may continue after discussion with, and assent from, the Medical Monitor. Participants should be rechecked each week until the AE returns to Grade 2.
- Participants experiencing Grade 4 AEs requiring permanent discontinuation of IP should be followed weekly until resolution of the AE and encouraged to complete the withdrawal and follow-up study evaluations as noted above. Any participant receiving at least one dose of CAB LA and /or RPV LA who discontinue IP / Withdraw will initiate treatment with HAART and enter the LTFU Phase for 52 weeks of follow up.
- Participants with Grade 4 asymptomatic laboratory abnormalities should be investigated for all potential non-drug related causes, and, following discussion with the Medical Monitor, may continue therapy if the Investigator has compelling evidence that the toxicity is not related to IP, with the exception of liver chemistry stopping criteria (See Section 7.4.5.1). An in-clinic follow-up visit will be performed approximately 2-4 weeks after the last dose of study medication if AEs, SAEs, or laboratory abnormalities considered potentially harmful to the participant are ongoing at the last on-study visit. Isolated Grade 4 lipid abnormalities do not require withdrawal of IP.

#### 7.4.5. Specific Toxicities/Adverse Event Management

General guidelines for the management of specific toxicities that are considered to be associated with treatment of HIV patients.

Participants who permanently discontinue study drug for reasons of toxicity should be followed weekly until resolution of the AE and encouraged to complete the withdrawal and Follow-up study evaluations as noted in Section 7.4.3.3.

##### 7.4.5.1. Liver Chemistry Stopping and Follow-up Criteria

Liver chemistry threshold stopping criteria have been designed to assure participant safety and to evaluate liver event etiology during administration of study drug and the follow-up phase. All Phase 3 participants who meet liver stopping criteria will be adjudicated by the ViiV Safety and Labelling Committee (VSLC) – resulting in a case summary, adjudication, and management plan. The VSLC contains an external expert hepatologist, familiar with both DILI and cabotegravir, who will participate in this review. This committee meets on a 3-weekly basis, and can be convened on an ad hoc basis as needed.

##### 7.4.5.2. Diarrhea

Participants with Grade 1 or 2 diarrhea may continue study treatment without interruption. Participants with diarrhea of any toxicity grade may be treated symptomatically with anti-motility agents; however, the recommended daily dose of the chosen anti-motility agent must not be exceeded. If symptoms persist or get worse on the

recommended daily dose of the chosen anti-motility agent then the anti-motility agent must be discontinued and consultation made with the Medical Monitor.

For participants with Grade  $\geq 3$  diarrhea that is unresponsive to the recommended dose of the anti-motility agents and for which an alternative etiology (e.g., infectious diarrhea) is not established, the treatment with the anti-motility agent and IP must be interrupted until resolution of diarrhea to Grade  $\leq 2$  or Baseline, after which IP and background ART may be resumed after discussion and agreement with the Medical Monitor. If Grade  $\geq 3$  diarrhea recurs within 28 days upon the resumption of IP, the IP should be permanently discontinued and the participant withdrawn from the study. Any participant receiving at least one dose of CAB LA and /or RPV LA who discontinue IP / Withdraw will initiate treatment with HAART and enter the LTFU Phase for 52 weeks of follow up.

If loperamide is used for treatment of diarrhea, local prescribing information should be followed with respect to dose and frequency of administration. Loperamide dosing should not exceed local prescribing information.

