**Participants must be discontinued from study treatment for any of the following reasons:**

- Participants who are not eligible to continue into the Maintenance Phase.
- Participants who are not eligible, or do not wish to continue on to the Extension Phase.
- Virologic withdrawal criteria as specified in Section 5.5.4 are met;
- Participant requires substitution of ART;
- Participant requires substitution or dose reduction of CAB LA or RPV LA (oral bridging supply and potential for a second loading dose may be permissible following discussion with the Medical Monitor).
- Liver toxicity where stopping criteria are met and no compelling alternate cause is identified (see Section 5.5.1);
- Renal toxicity are met and no compelling alternate cause is identified;
- QT interval (QTc) interval >550 msec from three or more tracings separated by at least 5 minutes and considered causally related to IP.
- Grade 4 clinical AE considered causally related to study drug;
- Participant has a Grade 3 or higher rash or Grade 2 rash with evidence of systemic involvement and no compelling alternative cause is identified
- Participant withdrew consent

Efficacy data for participants withdrawing from the study will be considered evaluable up to the point at which they are withdrawn using the same criteria for evaluability as for participants who complete the study.

Safety data for all participants who receive any amount of study drug, including participants who withdraw from the study, will be included in evaluations of safety.

All data from the Withdrawal visit will be recorded, as they comprise an essential evaluation that should be done prior to discharging any participant from the study.

The following actions must be taken in relation to a participant who fails to attend the clinic for a required study visit:

- a. The site must attempt to contact the participant and re-schedule the missed visit as soon as possible.
- b. The site must counsel the participant on the importance of maintaining the assigned visit schedule and ascertain whether or not the participant wishes to and/or should continue in the study.

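### Grade 4 diarrhea: Section 7.4.5.2 permits study drug to be resumed, while Section 7.4.4.4 (and Section 5.5, if the event is judged related) requires permanent discontinuation

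*Protocol*

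**What the plan says.** **Section 7.4.5.2 (Diarrhea)** sets one rule for Grade 3 and above. It applies to "diarrhea that is unresponsive to the recommended dose of the anti-motility agents and for which an alternative etiology (e.g., infectious diarrhea) is not established". In that case "the treatment with the anti-motility agent and IP must be interrupted until resolution of diarrhea to Grade" 2 or lower, or to Baseline, "after which IP and background ART may be resumed after discussion and agreement with the Medical Monitor". Permanent discontinuation comes in only if diarrhea of Grade 3 or higher returns within 28 days of resumption. A first Grade 4 episode gets no separate treatment.

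**Section 7.4.4.4 (Grade 4 Toxicity/Adverse Event)** states: "Participants who develop a Grade 4 AE or toxicity must have IP permanently discontinued". For a clinical event it leaves one way out: "if the Investigator has compelling evidence that the AE is not causally related to the IP, dosing may continue", after discussion with the Medical Monitor and with the Medical Monitor's assent.

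**Section 5.5 (Withdrawal/Stopping Criteria)** lists reasons for which study treatment must be discontinued. One item is: "Grade 4 clinical AE considered causally related to study drug".

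**Endpoints and analysis.** Sections 1.2 and 3 make the proportion discontinuing because of adverse events a secondary endpoint. Sections 1.3 and 4.1 define the key secondary endpoint, HIV-1 RNA below 50 c/mL at Week 48, with discontinuation counted as failure.

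**The concern.** A participant has a first episode of Grade 4 diarrhea, anti-motility treatment has not worked, and no other cause has been found. A site that opens 7.4.5.2 reads that study drug is interrupted and may be restarted. A site that opens 7.4.4.4 reads that study drug is stopped for good.

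The main stake is participant safety. The protocol gives two answers on whether treatment ends after an event of the highest severity grade that 7.4.4 provides for.

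The secondary stake is the data. A permanent stop enters the proportion discontinuing because of adverse events, and a stop before the Week 48 assessment can turn a responder into a failure in the key secondary endpoint. An interruption followed by resumption does neither by itself. If sites follow different sections, these two proportions partly reflect which section was read.

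**Working it through.** No sample-size or power figure is involved, and the protocol states no figure to reproduce. The check sets the rules side by side and then works out the weight of one participant.

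**Step 1. What each section does with diarrhea that has not responded and has no other established cause**

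| Case | 7.4.5.2 | General severity rule (7.4.4) | 5.5 | Result |
|---|---|---|---|---|
| A. First Grade 4 episode, judged related | Interrupt; may resume with Medical Monitor agreement | Permanent discontinuation | Discontinuation required | 7.4.5.2 permits what the other two forbid |
| B. First Grade 4 episode, not judged related, but no compelling evidence against causality | Interrupt; may resume | Permanent discontinuation | Not triggered | 7.4.5.2 permits what 7.4.4.4 forbids |
| C. First Grade 4 episode, compelling evidence against causality | Interrupt; may resume | Dosing may continue with the Medical Monitor's assent | Not triggered | Can be reconciled |
| D. Grade 3, judged related or possibly related | Interrupt; may resume at Grade 2 or lower, or Baseline | Withhold; may restart at Grade 2 or lower | Grade 4 item not triggered | Consistent |

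The conflict sits in cases A and B. The condition that brings 7.4.5.2 into play, no other cause established, describes the events for which the exception in 7.4.4.4 will ordinarily be hardest to meet.

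**Step 2. Does any text settle the order?**

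- Section 7.4.5 is introduced as general guidelines and does not say that it overrides 7.4.4 or 5.5.
- Where the general rules were meant to yield, they say so. Sections 7.4.4.3 and 7.4.4.4 except isolated lipid abnormalities, and 7.4.5.3 repeats that exception, so the general and specific rules agree there. Diarrhea has no counterpart.
- The list in Section 5.5 names liver, renal, QTc and rash criteria alongside its Grade 4 item. It makes no exception for diarrhea.

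**Step 3. Weight of one participant**

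Inputs: about 1020 participants randomized 1:1 (Sections 1.3 and 4.1).

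- Per arm: 1020 / 2 = 510.
- One participant: 1 / 510 = 0.00196, or about 0.20 percentage points of that arm's proportion.

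This applies to the adverse-event discontinuation proportion. It applies to the key secondary proportion only if the stop falls before the Week 48 assessment and the participant would otherwise have counted as below 50 c/mL. The protocol gives no rate for such diarrhea, so no expected number is calculated.

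**The case against.** **A permissive and a mandatory rule can both be obeyed.** Section 7.4.5.2 says only that drug may be resumed, and only with the Medical Monitor's agreement. If the event is judged related, Section 5.5 governs and the participant stops. This stands in part. Section 5.5 bites only on a judgment of causality, which is a different test from whether another cause has been established, and a careful reader can satisfy both sections by stopping. But 7.4.5.2 does not send the reader to the stricter rule, and 7.4.4.4 reaches further than 5.5: it also covers events not judged related when compelling evidence against causality is lacking.

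**No established alternative is not the same as no compelling evidence.** Section 6.9.1 notes that both long-acting drugs may be measurable for more than a year after injection, so resolution during continued exposure could bear on causality. This is right, and it is case C above. It leaves cases A and B untouched.

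**The specific rule should prevail over the general one.** This is a natural reading, but the text at hand does not state it, and the written lipid exception points the other way.

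**Sites do not decide alone.** Section 6.9 requires interruption and resumption decisions to be discussed with the Medical Monitor in advance. This stands and reduces variation between sites. A reader might infer from the open-label design that the choice would be biased by arm; the documents give no evidence of that. The Medical Monitor still works from two rules.

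**A tempting stronger reading concerns Grade 3.** A reader might infer that 7.4.5.2 keeps Grade 3 participants on drug until anti-motility treatment fails, against 7.4.4.3, under which participants with a Grade 3 event "which the Investigator considers related or possibly related to the IP, should have the IP withheld and be rechecked each week". The text does not support this. Section 7.4.5.2 gives leave to continue without interruption to Grades 1 and 2 alone. Its statement that "Participants with diarrhea of any toxicity grade may be treated symptomatically with anti-motility agents" concerns symptomatic treatment, not continued dosing. On Grade 3 diarrhea that is responding or has only just begun treatment it is silent, so 7.4.4.3 applies. Where 7.4.5.2 does require a hold, the two agree (case D).

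**Conclusion.** The protocol is inconsistent on one point: whether study drug may be resumed after a first Grade 4 episode of diarrhea that has not responded to treatment and has no other established cause. Section 7.4.5.2 permits it. Section 7.4.4.4 forbids it unless there is compelling evidence against causality, and Section 5.5 forbids it if the event is judged related.

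This matters mainly as a patient-safety ambiguity. Its statistical reach is limited to the adverse-event discontinuation proportion and, for stops before Week 48, the key secondary endpoint, at about 0.2 percentage points of one arm per affected participant. The number affected is probably small but cannot be derived from the protocol. No effect on the primary conclusion is claimed.

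The conclusion assumes that no precedence statement stands in the later part of the protocol, which was not available. It does not extend to Grade 3 diarrhea.

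**What to change.** Reconcile Section 7.4.5.2 with Sections 7.4.4.4 and 5.5 for Grade 4 diarrhea. Any one of three edits would do:

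- state in 7.4.5.2 which grades its interrupt-and-resume rule governs, with a cross-reference to 7.4.4.4 for the rest;
- write a diarrhea exception into 7.4.4.4 and 5.5, as is done for lipids in 7.4.4.4;
- add a sentence saying whether 7.4.4 and 5.5 or 7.4.5 prevails when they differ.

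Which rule should apply is a clinical decision for the sponsor's clinicians, and this review takes no position on it. The cost is one clause in the protocol, with no new data and no additional participants.
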